## 2.4 Potential Risks and Benefits

### 2.4.1 Potential Risks

The research involves minimal risks.

Loss of confidentiality presents minimal risk. Specimens will be identified by subject ID only linking data for subject ID will be kept in locked cabinet accessible only to the clinical research staff.

*Fecal sample will be collected from the diaper and presents no risk to the participant.*

Sugar solution- No risks have been reported in the literature from ingesting an isotonic solution of sugar (3-15). A similar simple sugar, sucrose (56), is given in higher doses for pain relief with fewer adverse effects than water placebo.

#### **2.4.2 Known Potential Benefits**

There are no known potential benefits to participants. The ability to measure increased intestinal permeability would indicate an infant has a leaky gut, and may be at increased risk for NEC. The potential risks from specimen collection are equivalent to those of normal clinical care.

#### **2.4.3 Risk/Benefit Ratio**

Despite improvements in neonatal intensive care, the birth weight-specific incidence of NEC has not changed over the past 2 decades. However, the total burden of disease is increasing due to increased survival of very immature infants. Mortality remains high and survivors experience significant morbidity including post-surgical short bowel syndrome and its consequences (prolonged dependence on total parenteral nutrition, recurrent infections, poor growth, and liver failure), prolonged hospitalization, and long-term neurodevelopmental impairments. Development of an *in vivo* measurement to identify infants with increased intestinal permeability, who are at high risk for NEC, will facilitate clinical trials of potential preventive therapies. There may be risks from the research that are not known.

### **2.5 Study Objectives**

The proposed study will evaluate the intestinal permeability measured by the urinary La/Rh ratio at one timepoint between d7-10 of life in 200 preterm infants 24-32 weeks gestation in preparation for a future study of probiotics to improve intestinal permeability in this population.

**Primary Objective:** To estimate mean, variance, and quantiles in IP measured by urinary Lactulose/Rhamnose ratio at 7-10d of life in neonates born between 24 and 32 weeks of gestational age.

**Secondary Objectives:**

- 1) To assess stool microbiome characteristics in association with intestinal permeability in preterm infants measured by the urinary lactulose/rhamnose ratio

- 2) *To analyze the correlation of stool calprotectin, sIgA, and lactoferrin to urinary lactulose/rhamnose ratio and stool microbiome characteristics in neonates born between 24 and 32 weeks of gestational age.*

### **3 STUDY DESIGN**

The study is a specimen collection study. Participants will include neonates admitted to the Neonatal Intensive Care Unit at the University of Maryland Medical Center, Baltimore, MD. The study will not test any type of device or treatment but is designed to accrue information.

#### **3.1 ENDPOINTS**

#### **3.2 Study Outcome Measures**

The study outcome measures will be intestinal permeability (quantitative) and leaky gut (binary), 1) increased levels of urine Lactulose/Rhamnose [La/Rh] ratio  $>0.05$  will identify infants with increased intestinal permeability (IP).

**3.3 Description of Sub-studies:** Not applicable

## 4 STUDY POPULATION

All admissions to the University of Maryland Medical Center (UMMC) NICU <5 d age and gestational age 24-32 weeks will be screened for study eligibility and parental consent of eligible subjects will be obtained. Two hundred total subjects will be recruited. The combined NICU population is approximately 59% male with an ethnic distribution of 65% African-American, 33% Caucasian and 2% other. Subjects will not be excluded based on gender, race or ethnicity.

### 4.1 Inclusion Criteria

Inclusion criteria will include

- 1) < 5 days
- 2) Gestational age 24-32 weeks

### 4.2 Exclusion Criteria

Exclusion criteria will include:

- 1) Non-viability or planned withdrawal of life support;
- 2) Triplet or higher order multiple;
- 3) Severe asphyxia (Apgar <3 at 5 min and cord pH <7.0);
- 4) Lethal chromosome abnormalities;
- 5) Cyanotic congenital heart disease;
- 6) Intestinal atresia or perforation;
- 7) Abdominal wall defects;
- 8) Significant GI dysfunction (e.g. heme-positive stools, abdominal distension (girth >2 cm baseline), or bilious emesis/aspirates.
- 9) *Infants with galactosemia or other forms of galactose intolerance*

### 4.3 Randomization

Not randomized

### 4.4 Blinding

Not blinded

## **4.5 Withdrawal**

### **4.5.1 Reasons for Withdrawal**

Subjects may be withdrawn from the study for the following reasons:

- 1) At the request of the subject's parent(s) or guardian(s), or at the request of other legally authorized representative;
- 2) If, in the investigator's opinion, continuation in the study would be detrimental to the subject's well-being;
- 3) At the request of the IRB or Safety Monitor.

### **4.5.2 Handling of Withdrawal**

Subjects who discontinue due to being withdrawn or lost to death will be replaced. Data and specimens will be de-identified and remain as part of the study.

## **4.6 Termination of the Study**

The study may be terminated:

- 1) At the request of the IRB or Safety Monitor
- 2) If the principal investigator is unable to continue with the study and a suitable replacement is not identified.

## 5 INVESTIGATIONAL PRODUCT(S)

### 5.1 Study product description

A 1mL/kg La/Rh solution (8.6 g of lactulose + 140 mg of rhamnose/100mL) will be used to assess intestinal permeability. Lactulose is a synthetic disaccharide formed from fructose and galactose. Rhamnose is a naturally occurring sugar.

Lactulose will be obtained as Kristalose from Cumberland Pharmaceuticals [name] ([www.cumberlandpharma.com](http://www.cumberlandpharma.com)) and is listed in the U.S. Pharmacopoeia.

Rhamnose will be obtained from Saccharides, Inc. [name].

Detailed instructions for preparation, storage and handling of the sugar solution can be found in the Manual of Procedures.

Administration details can be found in Section 6.

## 6 STUDY PROCEDURES / EVALUATIONS / SCHEDULE

### 6.1 Clinical/Laboratory Evaluations and Study Schedule

Informed consent will be obtained before any clinical evaluations are performed. Specific details of assay performance and calibration are listed in the MOP.

### 6.2 Screening (*include allowable time window*)

After receiving a HIPAA waiver from the IRB, clinical PI and staff will screen all new admittances to the NICU for eligibility criteria. Study interventions must be able to begin within 24 hours of enrollment. Informed consent must be signed before any study procedures are begun.

### 6.3 Enrollment/Baseline (*include allowable time window*)

After consent and HIPAA forms are signed, chart will be reviewed and history will be recorded. Medical history will be obtained from the chart and eligibility criteria will be confirmed.

Prior to Lactulose/rhamnose sugar probe dosing, the subject will have a complete physical exam including vital signs, weight, height, and head circumference.

### 6.4 Study Visits (*include allowable time window for each study visit*)

#### Postnatal day 5 (or within 24 hours of enrollment)

- ∞ Begin collecting available stool samples for microbiome, calprotectin, sIgA, and lactoferrin analysis
- ∞ Medication history will be collected from the chart.
- ∞ Complete physical exam including vital signs, weight, height, and head circumference.

#### Postnatal d7-10

- ∞ In vivo IP will be determined by means of the urine La/Rh test. Briefly, preterm neonates will be administered a 1 mL/kg La/Rh solution (8.6 g of lactulose + 140 mg of rhamnose/100 mL) via a clinically indicated OG or NG tube. The La/Rh solution will be prepared by the Investigational Drug Pharmacy (IDS) and administered by gavage. Starting at the time of the dose of the La/Rh solution, urine will be collected for a 4-hour period with cotton balls. If a participant does not require an OG/NG tube the solution will be administered orally by nippling.
- ∞ Continue collecting available stool samples daily until PND14 and single sample on PND21 for microbiome, calprotectin, sIgA, and lactoferrin analysis. Record daily weight, and weekly height, and head circumference.

- ∞ Demographic and clinical data will be collected from the chart.
- ∞ Collect adverse events from medical chart.

#### **6.5 Follow-up Visit(s) (include allowable time window)**

*Not applicable.*

#### **6.6 Unscheduled Visit(s)**

*Not applicable*

#### **6.7 Early Termination (include allowable time window)**

If early termination occurs the assessments from the final visit should be completed if the parent/LAR is willing. The physical exam and data collection regarding adverse events medication history should be collected at a minimum. If possible, the La/Rh should be administered and urine and serum should be collected.

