#### **6.8 Final Study Visit (include allowable time window)**

##### **PND21 (± 2d) or discharge/transfer whichever comes first**

- ∞ *Final collection of stool samples for analysis*
- ∞ Medication history including the number of packed red blood cell transfusions and total volume received will be collected from the chart
- ∞ *Record daily weight, and weekly height, and head circumference.*
- ∞ Collection of adverse events from medical chart.

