#### **6.9 Product Administration (include allowable time windows)**

Each enrolled preterm neonates will be administered a 1 mL/kg La/Rh solution (8.6 g of lactulose + 140 mg of rhamnose/100 mL) via a clinically indicated OG or NG tube once between 7-10 d of age. The La/Rh solution will be administered by gavage with an enteral feed. Total volume of La/Rh ingested will be recorded. Urine will be collected for a 4-hour period *with cotton balls*. Total volume of urine during the 4 hour collection will be recorded. The urine will be aliquoted and 4 ml of urine saved for analysis. Nursing staff in the NICU will be trained in the procedures prior to study initiation. Only trained NICU staff will be allowed to be responsible for administering the La/Rh solution and collecting the urine. A minimum of 2 ml of urine will be collected. If urine leaks around the cotton balls, then the diaper will be weighed and the diaper weight will be used to estimate the urine volume for the 4 hour collection period. If less than 2 ml urine is collected, then the test will be repeated on another day within the 7-10d window by

administering 1 ml/kg La/Rh solution (8.6g of lactulose + 140 mg of rhamnose/100mL) via an OG/NG tube followed by a 4 hour urine collection. The urine will be stored at -80°C until processed. The sugars will then be measured in urine by HPLC.

Urine La and Rh will be measured in the lab of our collaborator [name] from the University of Calgary, Canada.

*Stool calprotectin, sIgA, and lactoferrin will be measured by commercial ELISA kits.*

Rescue Therapy- NA

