### **6.10.2 Specimen Shipment**

Research staff will transport specimens collected at the University of Maryland Medical Center to the appropriate laboratory on campus. Specimens collected at Mercy Medical Center will be frozen and transported monthly to the laboratory of [name]. Aliquots of urine for La and Rh measurements by HPLC will be shipped to our collaborator [name] at the University of Calgary, Canada, for HPLC. All specimens will be accompanied by a shipping invoice indicating the sample ID and the chain of custody. Specific transport procedures are detailed in the MOP.

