### 10.5 Safety Review *(if applicable)*

## 10.6 Final Analysis Plan

**Primary Objective:** To estimate mean, variance, and quantiles in IP measured by urinary Lacutlose/Rhamnose ratio in in neonates born between 24 and 32 weeks of gestational age.

Sample quantiles of the distribution of IP (as measured by urine LA/Rh ratio) will be calculated at each time point. In addition, we will use mixed effects models to estimate the mean and variance of urine La/Rh. By including other terms in the model we will be able to assess whether high IP (La/Rh ratio  $>0.05$ ) is affected by gestational age, birthweight, sex or *feeding type (mother's own breast milk only, donor breastmilk, preterm formula only, or both breast milk and preterm formula).*

**Secondary Objective:** To evaluate the performance of stool calprotectin, sIgA, and lactoferrin as markers for intestinal permeability *in vivo* as established by the gold standard urine La/Rh in preterm neonates.

**Assessing the relationships between stool markers and urine La/Rh ratio:** To quantify the association between stool calprotectin, sIgA, and lactoferrin, and urine La/Rh ratio, we will calculate Pearson Correlation Coefficients. If the distribution of either variable exhibits substantial skewness we will substitute Spearman Correlation Coefficients. In addition, we will perform sub-group analyses by gestational age or birthweight.

**Assessing the sensitivity and specificity of calprotectin, sIgA, and lactoferrin for identifying children with leaky gut syndrome using an ROC analysis.** Leaky gut syndrome will be defined as having a urinary La/Rh ratio of greater than 0.05 at 7-10 d (12). Using this definition, we will assess the sensitivity, specificity, and predictive value of calprotectin, sIgA, and lactoferrin on each day for identifying those with leaky gut syndrome. An analogous calculation will be made to estimate specificity. We will perform these calculations for a large range of cut-offs for the stool markers, and summarize the findings using an ROC curve. The area under the ROC curve (AUC) will be calculated using an empirical approach to provide an overall summary measure of the performance of **calprotectin, sIgA, and lactoferrin** as measures for leaky gut syndrome.

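### Section 6.7 asks for serum at early termination, but nothing else in the current protocol draws, assays or analyses blood

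*Combined protocol and SAP*

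**What the plan says.** Section 6.7 (Early Termination) first asks for the final-visit assessments if the parent or representative agrees. It then sets a minimum of physical examination, adverse events and medication history. It ends with: "If possible, the La/Rh should be administered and urine and serum should be collected".

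The scheduled visits ask for the following specimens:

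- Postnatal day 5 (section 6.4): "Begin collecting available stool samples for microbiome, calprotectin, sIgA, and lactoferrin analysis".
- Postnatal days 7 to 10 (section 6.4): a 4-hour urine collection after the sugar dose, and stool: "Continue collecting available stool samples daily until PND14 and single sample on PND21".
- Postnatal day 21, or discharge or transfer if earlier (section 6.8): "Final collection of stool samples for analysis".

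On assays, section 6.9 says "The sugars will then be measured in urine by HPLC" and "Stool calprotectin, sIgA, and lactoferrin will be measured by commercial ELISA kits". The shipment section (6.10.2) names one specimen for a specific assay: "Aliquots of urine for La and Rh measurements by HPLC will be shipped to our collaborator". The marker analysis in section 10.6 is set up "To quantify the association between stool calprotectin, sIgA, and lactoferrin, and urine La/Rh ratio".

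**The concern.** Section 6.7 is a current instruction to study staff, and it names a specimen that the rest of the protocol never uses. A blood sample needs a purpose, a volume, a handling route and a risk statement, and the protocol gives none of these for serum.

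What is at stake is conduct and protection of the infants, not inference. The population is 24 to 32 weeks' gestation. One of the three withdrawal grounds in section 4.5.1 is the investigator's view that staying in the study would harm the infant, so the instruction can reach an infant already judged vulnerable. Section 2.4.1 describes the research as minimal risk and covers confidentiality, stool taken from the diaper and the sugar solution; blood sampling is not among them. Section 10.8 counts any noncompliance with the protocol as a deviation, so staff who could draw serum and do not are also in an awkward position.

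**Working it through.** No calculation is involved and the plan gives no figure to reproduce. The check takes each part of the protocol that could support a serum sample and asks whether it does.

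| Part of the protocol | What it covers | Serum or blood sample? |
|---|---|---|
| Visits (6.4, 6.8) | Stool at all three; urine at days 7 to 10 | 0 of 3 visits |
| Urine assays (6.9) | Lactulose, rhamnose | 0 of 2 |
| Stool assays (6.9, 10.6) | Calprotectin, sIgA, lactoferrin, 16S sequencing, quantitative PCR, metabolome | 0 of 6 |
| Objectives (2.5) | Urine ratio; its relation to the stool microbiome and stool markers | None |
| Analyses (10.6) | Urine ratio; stool markers against it; classifier from bacterial abundance and neonatal data | None |
| Shipment (6.10.2) | Only urine is named for an assay | None |
| Risks (2.4.1) | Confidentiality, diaper stool, sugar solution | None |
| Appendix A | Eligibility, consent, physical exam, history, medications, adverse events, La/Rh test, urine, stool | 0 of 9 rows |

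Named laboratory measurements: 2 in urine + 6 in stool = 8, of which 0 use serum. Section 10.6 also mentions a fecal calprotectin biochemical test. If that is separate from the ELISA in section 6.9, the total is 8 + 1 = 9, still with 0 in serum. The metabolome is prepared from fecal material, so it does not supply a use for serum either.

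Several more general passages might be read as supporting a draw:

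- Section 2.4.2 has one sentence equating specimen-collection risk with that of ordinary care. It is not limited to stool or urine, but it names no blood sample.
- Section 7.4.1 refers to severity tables for laboratory values (Appendices D and E), and section 10.7.1 mentions clinical laboratory data. Neither names a serum assay or a study draw.
- Appendix C lists safety laboratory tests in a checklist that applies only where relevant to the study. It does not create a test.
- Section 13.4 covers future use of stored specimens in general. It sets no serum sample, volume or time.

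The conflict therefore lies between section 6.7 and the rest of the current body text. The revision history is not needed to establish it. That history does suggest the origin: the version 2.0 entry ended the blood draws for zonulin, so the serum wording in 6.7 looks like a remnant.

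On exposure, discharge or transfer before day 21 is handled as the final visit under section 6.8. Section 6.7 is therefore left mainly with withdrawals under 4.5.1 and study termination under 4.6. The documents give no expected number of either.

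**The case against.** The best case on the other side is that the instruction will do little in practice. It is conditional and sits outside the stated minimum for early termination. The section opens by deferring to the parent's willingness. The investigator who judged that the infant should leave would also judge what is feasible. The revision history tells any reader that blood draws have stopped, and every visit section agrees.

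Much of this stands as a limit on consequence: an actual draw is possible rather than likely. It does not remove the error. The condition decides when serum is taken but gives the sample no purpose, and the parental-willingness clause belongs to a different sentence from the one that names serum. A revision entry does not correct operative text that still says otherwise.

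Two narrower points are fair. Because of the general sentence in section 2.4.2, the accurate claim is that there is no *blood-specific* risk statement. Appendix A is also weak evidence taken alone: in the available text it has no early-termination column, and its urine row carries no mark at any visit although urine is plainly collected. The conclusion does not depend on it, because the visits, assays and analyses all agree without it.

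**Conclusion.** The concern holds. The serum instruction in section 6.7 conflicts with the rest of the current protocol, which contains no study blood draw, serum assay, serum analysis or blood-specific risk statement.

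Severity is low. Bias, power, type I error and sample size are unaffected, and the number of infants exposed cannot be derived from the documents. The practical gain from correcting it is that an infant leaving the study is not bled without a stated reason.

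The conclusion rests on the protocol text alone. The Manual of Procedures, to which section 6.10.1 leaves specimen management, the consent pages and Appendices D and E were not available, so a serum procedure described there cannot be excluded. If one exists, the protocol would still be silent on its purpose, timing and risk. The La/Rh and urine parts of the sentence are not in dispute, since sections 6.9 and 7.6.1 already govern every dose.

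**What to change.** Delete the words *and serum* from section 6.7, so that the sentence asks only for the La/Rh test and urine. A cross-reference there to sections 6.9 and 7.6.1 would be a convenience for staff, but it is optional and corrects no error.

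The cost is a two-word deletion, submitted with the next amendment. No assay, visit or analysis in section 10.6 changes. If the sponsor does want serum at early termination, the protocol should instead state the assay, volume, handling, analysis and blood-sampling risk; nothing in the current text suggests that this is intended.

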#### **6.8 Final Study Visit (include allowable time window)**

##### **PND21 (± 2d) or discharge/transfer whichever comes first**

- ∞ *Final collection of stool samples for analysis*
- ∞ Medication history including the number of packed red blood cell transfusions and total volume received will be collected from the chart
- ∞ *Record daily weight, and weekly height, and head circumference.*
- ∞ Collection of adverse events from medical chart.

#### **6.9 Product Administration (include allowable time windows)**

Each enrolled preterm neonates will be administered a 1 mL/kg La/Rh solution (8.6 g of lactulose + 140 mg of rhamnose/100 mL) via a clinically indicated OG or NG tube once between 7-10 d of age. The La/Rh solution will be administered by gavage with an enteral feed. Total volume of La/Rh ingested will be recorded. Urine will be collected for a 4-hour period *with cotton balls*. Total volume of urine during the 4 hour collection will be recorded. The urine will be aliquoted and 4 ml of urine saved for analysis. Nursing staff in the NICU will be trained in the procedures prior to study initiation. Only trained NICU staff will be allowed to be responsible for administering the La/Rh solution and collecting the urine. A minimum of 2 ml of urine will be collected. If urine leaks around the cotton balls, then the diaper will be weighed and the diaper weight will be used to estimate the urine volume for the 4 hour collection period. If less than 2 ml urine is collected, then the test will be repeated on another day within the 7-10d window by

administering 1 ml/kg La/Rh solution (8.6g of lactulose + 140 mg of rhamnose/100mL) via an OG/NG tube followed by a 4 hour urine collection. The urine will be stored at -80°C until processed. The sugars will then be measured in urine by HPLC.

Urine La and Rh will be measured in the lab of our collaborator [name] from the University of Calgary, Canada.

*Stool calprotectin, sIgA, and lactoferrin will be measured by commercial ELISA kits.*

Rescue Therapy- NA

## **6.10 Define Specimen Preparation, Handling, and Shipping**

### **6.10.1 Instructions for Specimen Preparation, Handling, and Storage**

Specimen management will be detailed in the MOP.

